11.1 Ethical and legal conduct of the study

The procedures set out in this protocol, pertaining to the conduct, evaluation, and documentation of this study, are designed to ensure that the sponsor and investigator abide by Good Clinical Practice (GCP) guidelines and under the guiding principles detailed in the Declaration of Helsinki. The study will also be carried out in keeping with applicable local law(s) and regulation(s).

Documented approval from appropriate IEC(s)/IRBs will be obtained for the center before start of the study, according to GCP, local laws, regulations and organizations. When necessary, an extension, amendment or renewal of the EC/IRB approval must be obtained. The Sponsor/Investigator will ensure a list of the EC/IRB members involved in the vote, and a statement to confirm that the EC/IRB is organized and operates according to GCP and applicable laws and regulations, is filed with the study documents.

Strict adherence to all specifications laid down in this protocol is required for all aspects of study conduct; the investigator may not modify or alter the procedures described in this protocol. However, the Sponsor/Investigator may implement a deviation from, or a change of, the protocol to eliminate an immediate hazard(s) to the trial subjects without prior IEC/IRB approval/favorable opinion. As soon as possible, the implemented deviation or change, the reasons for it and if appropriate the proposed protocol amendment should be submitted to the IEC/IRB.

Any deviations from the protocol must be explained and documented by the investigator. Details on discontinuation of the study can be found in Section 10.

11.2 Subject information and consent

All relevant information on the study will be summarized in an integrated subject information sheet and informed consent form provided by the sponsor/investigator.

Based on this subject information sheet, the investigator or designee will explain all relevant aspects of the study to each subject / legal representative or proxy consentor (if the subject is under legal protection), prior to his/her entry into the study (i.e. before any examinations and procedures associated with the selection for the study are performed or any study-specific data is recorded on study-specific forms).

The investigator will also mention that written approval of the IRB/IEC has been obtained.

Phase II Study of Perindopril and Regorafenib in mCRC (PARICCA)

Each subject / legal representative or proxy consentor will have ample time and opportunity to ask questions and will be informed about the right to withdraw from the study at any time without any disadvantage and without having to provide reasons for this decision.

Only if the subject / legal representative or proxy consentor voluntarily agrees to sign the informed consent form and has done so, may he/she enter the study. Additionally, the investigator and other information provider (if any) will personally sign and date the form. The subject / legal representative or proxy consentor will receive a copy of the signed and dated form.

The signed informed consent statement is to remain in the investigator site file or, if locally required, in the patient's note/file of the medical institution.

In the event that informed consent is obtained on the date that baseline study procedures are performed, the study record or subject's clinical record must clearly show that informed consent was obtained prior to these procedures.

If the patient is not capable of providing a signature, a verbal statement of consent can also be given in the presence of an impartial witness (independent of the sponsor and the investigator). This is to be documented by a signature from the informing physician as well as by a signature from the witness.

The informed consent form and any other written information provided to subjects / legal representatives or proxy consentors will be revised whenever important new information becomes available that may be relevant to the subject's consent, or there is an amendment to the protocol that necessitates a change to the content of the subject information and / or the written informed consent form. The investigator will inform the subject / legal representative or proxy consentor of changes in a timely manner and will ask the subject to confirm his/her participation in the study by signing the revised informed consent form. Any revised written informed consent form and written information must receive the IEC/IRB's approval / favorable opinion in advance of use.

11.3 Publication policy

BAYER acknowledges the interest of the study sponsors to publish the findings of the STUDY and is supportive towards such activity.

To ensure against inadvertent disclosure of unprotected INVENTIONS and CONFIDENTIAL INFORMATION, the study sponsors agree to comply to the following terms on publication:

Study Sponsors shall provide to BAYER any proposed publication or oral presentation relating to the STUDY or STUDY DRUG or the RESULTS (hereinafter called "PUBLICATION") at least sixty

Phase II Study of Perindopril and Regorafenib in mCRC (PARICCA)

(60) days prior to the intended submission or presentation of the PUBLICATION in order to allow BAYER to review it.

If BAYER does not notify Study Sponsors within sixty (60) days of BAYER's receipt of the intended PUBLICATION, Study Sponsors shall be free to publish.

BAYER may recommend any changes to the PUBLICATION it reasonably believes are necessary for scientific purposes. Study Sponsors agree that the implementation of such recommended changes shall not be unreasonably refused.

If BAYER informs Study Sponsors that such PUBLICATION could be expected to have an adverse effect on the confidentiality of any of BAYER'S CONFIDENTIAL INFORMATION, Study Sponsors shall prevent the PUBLICATION, unless the CONFIDENTIAL INFORMATION can be deleted from the PUBLICATION without detriment effect on the scientific correctness of the PUBLICATION.

If the PUBLICATION could in BAYER'S view have an adverse effect on the ability to obtain patent protection for any INVENTION, BAYER may request a delay of the PUBLICATION for a reasonable period of time in order to permit the preparation and filing of any desired patent application by or on behalf of BAYER, such period, however, not to exceed ninety (90) days.

Study Sponsors shall include a statement in any PUBLICATION that creation of the data was supported in part by BAYER.

The Study Sponsors will make the information regarding the study protocol publicly available on the internet at www.clinicaltrials.gov.

11.4 Compensation for health damage of subjects / insurance

BCCA maintains clinical trial insurance coverage for this study in accordance with the laws and regulations of the province and country in which the study is performed.

- Clarification that 12-lead ECG is required at D1 of each cycle and at EOT visit.
- Clarification that urinalysis is required at EOT visit.
- Removal of ECOG assessment and blood pressure measurement at Safety Follow-up Visit since this visit may be conducted via telephone.

Protocol Version 2.0 dated 20 September 2016

- Correction of minor typographical errors and formatting errors in the document.
- Update of Exclusion Criteria pertaining to previous or concurrent cancers. As this study is meant to be quite pragmatic, it is overly restrictive to require participants to have no other cancer within 5 years prior to study enrollment. Instead, only patients with a concurrent cancer requiring treatment that is distinct in primary site or histology from colorectal cancer may not be enrolled.
- Addition of Exclusion Criteria: Patients receiving systemic anticancer therapy including cytotoxic therapy, signal transduction inhibitors, immunotherapy, hormonal therapy and experimental or approved therapies during this trial or within 14 days before starting to receive study medication. Chemotherapy/radiation is cleared by 14 days and most patients need treatment quickly when they progress. The 30 days was from a global strict randomized trial CORRECT.
- Clarification of Exclusion Criteria pertaining to proteinuria. 24-hour urine protein test is only required if protein/creatinine ratio on a random urine sample preferably taken at

Phase II Study of Perindopril and Regorafenib in mCRC (PARICCA)

mid-morning results in a ratio greater than 30g/mol Creat. The 24-hour urine protein test should be performed to confirm Grade 3 or higher proteinuria (>3.5g/24 hours). Proteinuria is usually from bevacizumab which is given in first line. In PARICCA, participants receive regorafenib for third- or fourth-line treatment. Proteinuria is screened with urinalysis and the 24-hour urine protein test needs only to be done if >30g/mol.

- Clarification of Screening procedures in Section 7.1.2.1 Screening relating to quantification of proteinuria. If UPCR is found to be greater than ULN, then a 24-hour urine protein test should be performed to confirm Grade 3 or higher proteinuria (>3.5g/24 hours).
Proteinuria is usually from bevacizumab which is given in first line. In PARICCA, participants receive regorafenib for third- or fourth-line treatment. Proteinuria is screened with urinalysis and the 24-hour urine protein test needs only to be done if >30g/mol.
- Clarification of photography procedures in Section 7.1 Schedule of procedures. In previous version of protocol, it was not detailed that a total of approximately 8 photographs will be taken of the dorsal and plantar/palmer surfaces of each of the participant's hands and feet at each specified interval. The labeling procedures are also clarified in this amendment.
- On Day 1 of each cycle, the participant is to receive a Rash Diary to complete (Section 7.1.2.2 Treatment). In order to more adequately document the onset of rash during treatment, participants will be asked to complete a Rash Diary during each treatment cycle. Information collected through this Rash Diary will assist in assessing time to development of HFSR toxicity. The Rash Diary will be collected by the designated study personnel upon completion of the diary, following each treatment cycle.

Protocol Version 2.1 dated 07 December 2016

- Correction of minor typographical errors and formatting errors in the document.
- Change of Inclusion Criteria relating to alanine transaminase (ALT), aspartate aminotransferase (AST), and alkaline phosphatase (ALP). Patients with liver involvement of their cancer may be included if ALT, AST, and ALP are ≤ 5 times ULN. The rationale is to align with the eligibility in the CORRECT phase III trial of regorafenib.
- 7.1 Schedule of procedures (Page 43) – Clarification of the liver function tests required every week for the first cycle, every two weeks for the second cycle, at the start of each cycle after this, and at follow up visit.

Protocol Version 2.2 dated 08 February 2017

Phase II Study of Perindopril and Regorafenib in mCRC (PARICCA)

- List of abbreviations: Addition of ACE (angiotensin converting enzyme) and ARB (angiotensin receptor blocker).
- Clarification of exclusion criterion relating to pre-existing anti-hypertensive treatment. The exclusion criterion was: “Patient selection to exclude patients with pre-existing anti-hypertension treatment, in particular other ACE inhibitors....” The exclusion criterion is now: “Patients with pre-existing anti-hypertensive treatment with an ACE inhibitor or angiotensin receptor blocker (ARB) are to be excluded....” This update makes it clearer that patients may still be eligible for participation if they have controlled hypertension using an anti-hypertensive that is not an ACE inhibitor or ARB.

14. Appendices

14.1 RECIST

Response and progression will be evaluated in this study using the RECIST criteria version 1.1. (*Eisenhauer EA et al. 2009*) Changes in only the largest diameter (unidimensional measurement) of the tumor lesions are used.

Measurable Disease:

Tumor lesions: Measurable lesions are defined as those that can be accurately measured in at least one dimension (longest diameter to be recorded) with a minimum size of

- 10 mm by CT scan (CT scan slice thickness no greater than 5 mm) or MRI. If scans with slice thicknesses greater than 5mm are used, the minimum size should be twice the slice thickness.
- 20 mm by chest x-ray
- 10 mm caliper measurement by clinical examination (lesions which cannot be accurately measured with calipers should be recorded as non-measurable)

Malignant lymph nodes: To be considered pathologically enlarged and measurable, a lymph node must be ≥ 15 mm in short axis when assessed by CT scan (CT scan slice thickness recommended to be no greater than 5 mm). At baseline and in follow-up, only the short axis will be measured and followed.

Lytic bone lesions or mixed lytic-blastic lesions, with identifiable soft tissue components that can be evaluated by CT or MRI, can be considered as measurable lesions if the soft tissue component meets the definition of measurability.

All tumor measurements must be recorded in millimetres (or decimal fractions of centimetres). Tumor lesions situated in a previously irradiated area are not considered measurable unless there has been demonstrated progression in the lesion.

Non-Measurable Disease: All other lesions (or sites of disease), including small lesions (longest diameter <10 mm or pathological lymph nodes with ≥ 10 to < 15mm short axis) are considered non-measurable disease. Leptomeningeal disease, ascites, pleural/pericardial effusions, lymphangitic involvement of skin or lung, inflammatory breast disease, abdominal masses/abdominal organomegaly identified by physical examination that is not measurable by reproducible imaging techniques and blastic bone lesions are all non-measurable.

Target Lesions: All measurable lesions up to a maximum of 2 lesions per organ and 5 lesions in total, representative of all involved organs should be identified as *target lesions* and be recorded and measured at baseline. These 5 lesions should be selected on the basis of their size (lesions with the longest diameter), be representative of all involved organs and should be suitable for reproducible repeated measurements. A sum of the diameters (longest for non-nodal lesions, short axis for nodal lesions) for *all target lesions* will be calculated and reported as the baseline sum diameters. The baseline sum diameters will be used as reference to further characterize any objective tumor regression of the measurable dimension of the disease. If there are >5 measurable lesions, those not selected as *target lesions* will be considered together with non-measurable disease as *non-target lesions*.

Non-target Lesions: All non-measurable lesions (or sites of disease) plus any measurable lesions over and above the 5 listed as *target lesions*. Measurements are not required but these lesions should be noted at baseline and should be followed as “present”, “absent” or in rare cases “unequivocal progression”.

Best Response

All subjects will have their BEST RESPONSE on study classified as outlined below:

Complete Response (CR): Disappearance of all clinical and radiological evidence of tumor (both *target* and *non-target*). Any pathological lymph nodes (whether target or non-target) must have a reduction in short axis to < 10mm.

Partial Response (PR): At least a 30% decrease in the sum of diameters of target lesions taking as reference the baseline sum, no unequivocal progression of existing non-target lesions and no appearance of new lesions.

Stable Disease (SD): Steady state of disease. Neither sufficient shrinkage to qualify for PR nor sufficient increase to qualify for PD, no unequivocal progression of existing non-target lesions and no appearance of new lesions.

Progressive Disease (PD): At least a 20% increase in the sum of diameters of target lesions taking as reference the smallest sum on study (this includes the baseline sum if that is the smallest on study). In addition to the relative increase of 20%, the sum must also demonstrate

Phase II Study of Perindopril and Regorafenib in mCRC (PARICCA)

an absolute increase of at least 5mm. Unequivocal progression of existing non-target lesions or the appearance of one or more new lesions will also constitute progressive disease.

Table 1: Response for patients with Target and Non-Target Lesions

Target Lesions	Non-Target Lesions	New Lesions	Overall Response	Best Response for this category also requires
CR	CR	No	CR	
CR	Non-CR/Non-PD	No	PR	
CR	Not evaluated	No	PR	
PR	Non-PD or not all evaluated	No	PR	
SD	Non-PD or not all evaluated	No	SD	documented at least 6 wk. from enrollment
Not all evaluated	Non-PD	No	NE	
PD	Any	Yes or No	PD	
Any	PD	Yes or No	PD	
Any	Any	Yes	PD	

Subjects with a global deterioration of health status requiring discontinuation of treatment without objective evidence of disease progression at that time should be reported as “*symptomatic deterioration*”. Every effort should be made to document the objective progression even after discontinuation of treatment.

Table 2: Response for patients with Non-Target Lesions only

Non-Target Lesions	New Lesions	Overall Response
CR	No	CR
Non-CR/Non-PD	No	Non-CR/non-PD*
Not evaluated	No	NE
Unequivocal PD	Yes or No	PD
Any	Yes	PD

* Non-CR/non-PD is preferred over “stable disease” for non-target disease.

Methods of Measurement

The same method of assessment and the same technique should be used to characterize each identified and reported lesion at baseline and during follow-up.

Clinical Lesions - Clinical lesions will only be considered measurable when they are superficial (e.g. skin nodules, palpable lymph nodes) and ≥ 10 mm diameter as assessed using calipers. For the case of skin lesions, documentation by colour photography including a ruler to estimate the size of the lesion is recommended.

Chest X-ray - Lesions on chest X-ray are acceptable as measurable lesions when they are clearly defined and surrounded by aerated lung. However, chest CT is preferable.

CT / MRI - CT is the best currently available and reproducible methods to measure target lesions selected for response assessment. CT scans should be performed with cuts of 5 mm or less in slice thickness. When CT scans have slice thickness greater than 5 mm, the minimum size for a measurable lesion should be twice the slice thickness. MRI is also acceptable. This applies to the chest, abdomen and pelvis. Head & neck and extremities usually require specific protocols.

Ultrasound - Ultrasound is not useful in assessment of lesion size and should not be used as method of measurement. If new lesions are identified by ultrasound in the course of the study, confirmation by CT or MRI is advised.

Endoscopy / Laparoscopy - The utilization of these techniques for objective tumor evaluation is not advised.

Cytology / Histology - These techniques can be used to differentiate between PR and CR in rare cases (for example, residual lesions in tumor types such as germ cell tumors, where known residual benign tumors can remain). The cytological confirmation of the neoplastic origin of any effusion that appears or worsens during treatment when the measurable tumor has met criteria for response or stable disease is mandatory to differentiate between response or stable disease (an effusion may be a side effect of the treatment) and progressive disease.

14.2 NCI Common Terminology Criteria for Adverse Events

This study will utilize NCI Common Terminology Criteria for Adverse Events for toxicity and serious adverse event reporting. Version 4.03¹ will be used. Version 3.0 was used in the CORRECT trial, however Version 4.03 will be used for comparison to future studies.

¹ http://evs.nci.nih.gov/ftp1/CTCAE/CTCAE_4.03_2010-06-14_QuickReference_5x7.pdf

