5.1.1 Inclusion criteria

In order to be eligible, all inclusion criteria must be met.

A patient must:

- Understand, be willing to give consent, and sign a written informed consent form prior to undergoing any study-specific procedure
- Be male or female and ≥ 18 years of age
- Histological or cytological documentation of adenocarcinoma of the colon or rectum.
- Patients with metastatic colorectal cancer (Stage IV) previously treated with fluoropyrimidine-based chemotherapy, oxaliplatin, irinotecan, an anti-VEGF therapy, and, if *KRAS* wild type, an anti-EGFR therapy.

Phase II Study of Perindopril and Regorafenib in mCRC (PARICCA)

- Progression during or within 3 months following the last administration of approved standard therapies, or have experienced intolerance to previous therapy. Patients treated with oxaliplatin in an adjuvant setting should have progressed during or within 6 months of completion of adjuvant therapy. (Please note that in Canada patients are not re-challenged with oxaliplatin in the metastatic setting).
- Metastatic CRC patients with measurable or non-measurable disease
- Life expectancy of at least 3 months
- Have an Eastern Cooperative Oncology Group performance status of 0 or 1 (within 14 days prior to the initiation of study treatment)
- Have adequate bone marrow, liver function, and renal function as measured by the following laboratory assessments conducted within 7 days prior to the initiation of study treatment:
 - Total bilirubin \leq 1.5 times the upper limit of normal (ULN)
 - Alanine aminotransferase (ALT) and aspartate aminotransferase (AST) \leq 2.5 times the ULN ($<$ 5 times ULN for patients with liver involvement of their cancer)
 - Lipase \leq 1.5 times the ULN
 - Serum creatinine \leq 1.5 times the ULN
 - Glomerular filtration rate \geq 30 mL/min/1.73 m² according to the modified diet in renal disease abbreviated formula
 - International normalized ratio (INR) of prothrombin time (PT; PT-INR) and partial thromboplastin time (PTT) \leq 1.5 times the ULN
 - Platelet count \geq 100000 /mm³, hemoglobin (\geq 9 g/dL, absolute neutrophil count \geq 1500/mm³).
 - Alkaline phosphatase limit \leq 2.5 times the ULN ($<$ 5 times ULN for patients with liver involvement of their cancer)
- If female and of childbearing potential, have a NEGATIVE result on a pregnancy test performed a maximum of 7 days before initiation of study treatment

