- Patients with evidence or history of bleeding diathesis, including patients who have had a transfusion and/or radiographic endoscopic or elective operative intervention to control the bleeding or hemorrhage event within four weeks prior to the study.
- Non-healing wound, ulcer, or bone fracture.
- Renal impairment or failure requiring hemo-or peritoneal dialysis.
- Patients with severe hepatic impairment.
- Dehydration NCI-CTC version 4.03 grade $>$ 1.
- Substance abuse, medical, psychological or social conditions that may interfere with the patient's participation in the study or evaluation of the study results

Phase II Study of Perindopril and Regorafenib in mCRC (PARICCA)

- Any illness or medical conditions that are unstable or could jeopardize the safety of the study
- Interstitial lung disease with ongoing signs and symptoms at the time of informed consent.
- Persistent proteinuria of CTC Grade 3 or higher. Quantification of proteinuria done by urinary protein/creatinine ratio on a random urine sample preferably taken at mid-morning. If protein/creatinine ratio is greater than 30g/mol Creat, then a 24-hour urine protein test should be performed to confirm Grade 3 or higher proteinuria (> 3.5 g/24 hours).
- Patients unable to swallow oral medications
- Any malabsorption condition
- Unresolved toxicity higher than NCI-CTCAE (version 4.03) Grade 1 attributed to any prior therapy/procedure excluding alopecia and oxaliplatin induced neurotoxicity ≤Grade 2
- Patients who are hypersensitive to perindopril, as well as those hypersensitive to regorafenib, sorafenib, drugs in the same class or any ingredient in the formulation.
- Patients who cannot tolerate the full dose of perindopril (4 mg) for any reason.
- Patients receiving systemic anticancer therapy including cytotoxic therapy, signal transduction inhibitors, immunotherapy, hormonal therapy and experimental or approved therapies during this trial or within 14 days before starting to receive study medication.

In addition, patients will be excluded for the following reasons (From perindopril monograph). Patients with a history of hereditary/idiopathic angioedema, or angioedema related to previous treatment with an angiotensin converting enzyme inhibitor.

- Pregnant women or those planning to become pregnant, nursing women.
- Patients with hereditary problems of galactose intolerance, glucose-galactose malabsorption, or the Lapp lactase deficiency.

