Grade 1: Numbness, dysesthesia, paraesthesia, tingling, painless swelling, erythema or discomfort of the hands or feet which does not disrupt the subjects normal activities	Any	Maintain dose level and institute immediately supportive measures for symptomatic relief
Grade 2: Painful erythema and swelling of the hands or feet and/or discomfort which affects the subject's normal	1st occurrence	Consider decreasing dose by one dose level and institute immediately supportive measures. If no improvement, interrupt therapy for a minimum

Phase II Study of Perindopril and Regorafenib in mCRC (PARICCA)

Table 4 Dose Modifications for Hand-Foot Skin Reaction		
Skin Toxicity Grade (according to CTCAE version 4.03 "Palmar-plantar erythrodysesthesia syndrome")	Occurrence ^c	Suggested Dose Modification ^c
activities		of 7 days, until toxicity resolves to Grade 0-1. ^b
	No improvement within 7 days or 2nd occurrence	Interrupt therapy until toxicity resolves to Grade 0-1. When resuming treatment, treat at reduced dose level. ^b
	3rd occurrence	Interrupt therapy until toxicity resolves to Grade 0-1. When resuming treatment, decrease dose by one additional dose level. ^{a,b}
	4th occurrence	Discontinue therapy
Grade 3: Moist desquamation, ulceration, blistering or severe pain of the hands or feet, or severe discomfort that causes the subject to be unable to work or perform activities of daily living.	1st occurrence	Institute supportive measures immediately. Interrupt therapy for a minimum of 7 days until toxicity resolves to Grade 0-1. When resuming treatment, decrease dose by one dose level. ^b
	2nd occurrence	Institute supportive measures immediately. Interrupt therapy for a minimum of 7 days until toxicity resolves to Grade 0-1. When resuming treatment, decrease dose by one additional dose level. ^{a,b}
	3rd occurrence	Discontinue treatment permanently.
^a Subjects requiring > 2 dose reductions (< 80mg) should go off protocol therapy ^b If toxicity returns to Grade 0-1 after dose reduction, dose re-escalation is permitted at the discretion of the investigator ^c A more conservative dose modification approach, if medically indicated, is acceptable, but please contact the sponsor prior to making any changes.		

If no recovery after a 4-week delay, treatment will be discontinued permanently.

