7.1.2 Timing of assessments

7.1.2.1 Screening

The assessments required as part of Screening can be completed in one or more visits, as long as the assessments are completed within the time frames listed below.

The following procedures and assessments will be performed **within 28 days of starting study drug**:

- Obtainment of written informed consent. No screening procedures may be performed unless written informed consent has been obtained (see Section 11.2)
- Allocation of unique Study Identification Number
- Confirm pathologic documentation of a primary diagnosis of CRC.
- Radiological tumor assessment using the RECIST criteria, version 1.1 (see Appendix 14.1) must be performed. The radiological evaluation must include a CT or MRI of the chest, abdomen and pelvis and should meet the standard of care for the imaging of lesions in the respective organ system(s). A PET scan is not acceptable for radiological evaluation.
- All additional suspected sites of disease should be imaged. A CT or MRI scan of the head must be performed with appropriate contrast media if a patient is suspected of having brain metastases, or is symptomatic.
- Appropriate radiological evaluation should be obtained if bone metastases are suspected (e.g., bone scan).
- Complete medical history including demographics, allergies, prior surgery and prior chemo/radiation therapy with documentation of treatment response. See section 7.5.1.1 for detailed instructions on the differentiation between medical history and adverse events.
- Previous HFSR (or HFS) of any grade with other chemotherapy (yes/no response only, no chart review).
- 12-lead ECG

The following procedures and assessments will be performed **within 14 days of starting study drug**:

- ECOG performance status (Appendix 14.6).
- Physical examination including review of all organ systems, examination of pertinent organ systems, vital signs (heart rate, blood pressure, and temperature) weight and height.
- The blood pressure measurements must be performed in a consistent manner using a manual cuff on the same arm. Have the patient sit comfortably for 5 minutes with feet on the floor and arm supported at heart level prior to taking the evaluation. The assessment must be made with the patients in the sitting position using the same arm for all evaluations. Two additional measurements, taken 5 minutes apart, should be conducted if the first blood pressure is abnormal.

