8.3.1 Primary Endpoint

The primary endpoint of this study is proportion of patients with any grade HFSR toxicity. Toxicities will be evaluated used CTCAE v4.03 criteria.

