8.3.2 Statistical hypothesis and method of analysis

The primary analysis will be a comparison of the proportion of patients with any grade HFSR toxicity to 47% using the normal approximation z-test statistic and 2-sided 5% significance level. The statistical hypotheses are

H0: $P = 0.47$ versus H1: $P \neq 0.47$

where P is the proportion of any grade HFSR toxicity.

The study includes a single interim safety analysis after 10 patients have completed the study medication.

The proportion of patients having worst grade 3 HFSR toxicity will be determined along with the 95% confidence interval.

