8.7 Determination of sample size

A sample size of 34 patients achieves 80% power to detect a 50% reduction in all grades of HFSR toxicity (from 47% as seen in the CORRECT trial to 24%) using the normal approximation to the binomial distribution and a 2-sided 5% significance level.

9. Data handling and quality assurance

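### The primary test sets HFSR graded by CTCAE v4.03 against a 47% benchmark graded by v3.0 with no bridging, and the all-grade hypertension figure can largely reflect blood pressure at entry

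*Combined protocol and SAP*

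**What the plan says.** **HFSR.** Section 8.3.1 states: "The primary endpoint of this study is proportion of patients with any grade HFSR toxicity", with grading by CTCAE v4.03. Section 8.3.2 states: "The primary analysis will be a comparison of the proportion of patients with any grade HFSR toxicity to 47" per cent, by a normal-approximation z-test at the two-sided 5% level. Section 8.7 gives the source of the benchmark and the target: "from 47% as seen in the CORRECT trial to 24" per cent, with 34 patients and 80% power. Appendix 14.2 states: "Version 3.0 was used in the CORRECT trial, however Version 4.03 will be used for comparison to future studies".

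**Hypertension.** The proportion with hypertension of all grades is a secondary, descriptive endpoint (Sections 2.2 and 8.4). Table 5 in Section 6.4.2 sets Grade 1 at 120-139 systolic or 80-89 diastolic, Grade 2 from 140/90 and Grade 3 from 160/100. Section 5.1.2 excludes patients only above 150 systolic or 90 diastolic. Section 1.1 hypothesises that perindopril will probably reduce hypertension.

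**New or worsened.** Section 8.5 defines treatment-emergent events as those that arise or worsen after study drug starts. Section 7.5.1.1 records conditions present before consent and unchanged as medical history. Sections 8.3.1 and 8.4 cite neither rule.

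**The concern.** A single-arm test against a fixed external rate is meaningful only if the rate and the observed proportion count the same thing. Here the two are graded by different versions of the criteria. The one reason given for the change looks forward to later studies, while the primary comparison looks back to CORRECT. For an any-grade endpoint, everything depends on where Grade 0 ends and Grade 1 begins. If v4.03 draws that line elsewhere, the observed proportion would move with no effect of perindopril.

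For hypertension, a patient can be enrolled with a blood pressure that already falls in the Grade 1 range, or in the lower part of Grade 2. An all-grade proportion that counts such patients describes whom the trial enrolled more than what treatment did.

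**Working it through.** **Inputs.** From Sections 8.3.2 and 8.7: p0 = 0.47, p1 = 0.24, n = 34, two-sided 5%, 80% power, z-test. Assumed, because the documents do not give it: π, the any-grade HFSR rate under v4.03 if perindopril had no effect, varied from 42% to 52%.

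**1. The plan's sample size.** n = [1.960 × √(0.47 × 0.53) + 0.842 × √(0.24 × 0.76)]² / (0.47 − 0.24)² = (0.978 + 0.359)² / 0.0529 = 33.8, so 34. Approximate power at 34 is 80.2%. The stated figure reproduces.

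**2. When the test rejects.** The standard error under H0 is √(0.47 × 0.53 / 34) = 0.0856.
- 10/34 gives z = −2.05 and 11/34 gives −1.71.
- 22/34 gives z = 2.07 and 21/34 gives 1.72.

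The test therefore declares a reduction at 10 or fewer events and an increase at 22 or more.

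**3. Chance of each result if the v4.03 no-effect rate is π.** Exact binomial with n = 34. A false reduction is P(X ≤ 10 | π), a false increase is P(X ≥ 22 | π), and power for a true halving is P(X ≤ 10 | π/2).

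| π (assumed except 47%) | False reduction | False increase | Power for a halving |
|---|---|---|---|
| 42% | 9.3% | 0.6% | 91.7% |
| 46% | 3.7% | 2.2% | 86.2% |
| 47% (plan) | 2.8% | 2.9% | 84.5% |
| 48% | 2.2% | 3.7% | 82.8% |
| 52% | 0.65% | 9.4% | 74.8% |

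The 84.5% in the plan's row is for exactly half of 47%, which is 23.5%. At the planned 24%, exact power is 82.8%.

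A one-point shift either way is of little consequence. A five-point shift would be material: downward it roughly triples the false-reduction risk, and upward it costs about ten points of power and triples the false-increase risk. Nothing in the documents says which row applies.

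**4. Hypertension, passages side by side.** Entry permits readings up to 150/90. Table 5 puts 120-139/80-89 in Grade 1 and 140-159/90-99 in Grade 2. So the whole Grade 1 range is admissible at entry, as are a systolic reading of 140 to 150 and a diastolic reading of 90. Even if only worsening counts, a move from just under to just over 120/80 is a Grade 1 event. The documents do not give the distribution of blood pressure at entry, so no size is calculated. There is no formal test here, and type I error and power do not arise.

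**The case against.** **On the benchmark.** The protocol discloses the version change openly. Any consequence depends on v3.0 wording that is not in the documents, and the five-point shifts have no source. If the Grade 0/1 boundary is the same in both versions, nothing changes beyond one sentence. Section 7.3 also leaves the full variable list to a statistical analysis plan, which might address the matter. All of this limits the claim, but it does not remove the gap in the supplied text. A reader might infer that the test is biased, or that the contrast between 47% in CORRECT and 74.3% in CONCUR, with Grade 3 rates of 17% and 16.2%, shows a grading effect. The documents support neither: the populations differ, and no passage attributes the contrast to grading.

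**On symptoms carried in at entry.** A reader might also infer that the HFSR count is inflated by residual neuropathy. Patients were "previously treated with fluoropyrimidine-based chemotherapy, oxaliplatin, irinotecan, an anti-VEGF therapy"; the exclusion reads "Unresolved toxicity higher than NCI-CTCAE (version 4.03) Grade 1 attributed to any prior therapy/procedure excluding alopecia and oxaliplatin induced neurotoxicity" up to Grade 2; and Grade 1 in Table 4 begins "Numbness, dysesthesia, paraesthesia, tingling, painless swelling, erythema or discomfort of the hands or feet". Screening records "Previous HFSR (or HFS) of any grade with other chemotherapy (yes/no response only, no chart review"). If two such patients were counted, with 24% in the other 32, power would be P(Bin(32, 0.24) ≤ 8) = 64.5% rather than 82.8%. The documents do not support that reading:
- Section 2.2 treats HFSR as an adverse event and evaluates it at baseline.
- Section 7.5.1.1 records unchanged conditions from before consent as medical history.
- Section 8.5 counts only what arises or worsens.
- Table 4 is dose-modification text.
- The two patients are an assumption.

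What remains is a missing cross-reference in Section 8.3.1.

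**On hypertension.** The endpoint is descriptive, severity by grade is already planned, and the recording rules and the treatment-emergent title of Table 5 point to a new-or-worsened reading. That is fair. But the endpoint text does not state the rule, and even with it an all-grade figure is driven by the low Grade 1 threshold. The point stands as a modest improvement.

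**Conclusion.** The point holds in a limited form. The trial's one formal test compares proportions graded under different CTCAE versions. The stated reason does not cover that comparison, and the supplied text does nothing to bridge it. The size and direction of any effect are unknown. The figures of 9.3% (at an assumed 42%) and 74.8% (at an assumed 52%) show how sensitive the test is, not what is expected. The sample-size arithmetic is sound, and N = 34 stands if the comparison is like for like.

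The all-grade hypertension proportion can largely reflect blood pressure at entry, and so may say little about the hypothesis in Section 1.1. A reader should not go on to infer that it would mislead a test against CORRECT's 28%, because none is planned.

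The change should be made, with medium confidence. The new-or-worsened citation and the Version 4.2 wording in Section 6.4.2 are clarifications only.

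**What to change.** 1. **HFSR benchmark.** Before analysis, compare the Grade 0/1 HFSR boundary in v3.0 and v4.03. If it is the same, say so in the SAP and keep one grading. If it differs, record for each HFSR event whether it meets the v3.0 definition, test 47% on that basis, and report the v4.03 proportion alongside. The cost in that case is one CRF field, a second look at each HFSR event, amended wording in Sections 8.3.1 and 8.3.2, and two HFSR figures to explain.
2. **Hypertension.** Beside the all-grade figure, report the proportions new or worse than pre-dose Cycle 1 Day 1 at Grade 2 or above and at Grade 3 or above, with no claim of direct comparability with CORRECT's 28%. The cost is one table, since Table 7 already schedules blood pressure on Cycle 1 Day 1 and later.
3. **Clarifications.** Cite the Section 8.5 new-or-worsened rule in Sections 8.3.1 and 8.4. Reconcile Version 4.2 in Section 6.4.2 with the v4.03 named elsewhere. The cost is wording only.
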